13.5 TOLERABILITY OUTCOMES

- **13.5.1** Achiness. The SOWS-Gossop scale will be administered twice a day. Item 10 yields an ordinal measure of achiness. We will use mixed effects ordinal logistic regression models, with site and group as the main explanatory variables, to compare the groups on their probabilities of the different ordinal levels.
- **13.5.2_Anxiety.** Item 1 of the SOWS-Gossop yields an ordinal measure of anxiety, and we will compare the groups using mixed effects logistic regression models as for the Achiness item above.
- **13.5.3** Insomnia. The Insomnia Severity Index will be administered daily during detoxification, and yields a total score. We will compare the groups on the score using linear mixed effects models similar to those described for the primary outcome.

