Note: Study medication will be provided in blister packs that are prepared by the PENN Investigational Drug Service and shipped to all three study sites. For the University of Pennsylvania, each blister pack will have a patient randomization number and the dosing schedule for each time on each inpatient study day, as summarized in the Study Schematics 4.0 below. For the two external sites, patient randomization will be generated by the site pharmacy or designated unblinded person, who receives the blister packs from the PENN Investigational Drug Service with the dosing schedule for each day.

The doses for each time of each day will be in separate compartments. Lofexidine will be 0.18 mg pink tables; pregabalin or pregabalin placebo will be in capsules. Blue capsules will contain 100 mg pregabalin or placebo; green capsules will contain 25 mg pregabalin or pregabalin placebo. These medications have not been used together and it is likely that doses will need to be held or reduced due to side effects. The most likely side effect from lofexidine is hypotension and/or bradycardia. The most likely side effect from pregabalin is sedation. Thus, in the event of hypotension, the next scheduled dose of lofexidine can be reduced or withheld. A similar adjustment can be made for excessive sedation (POSS score of 3 or 4; difficult to arouse, slurred speech, etc.) For the PENN site, medication counts will be done by the Investigational Drug Service (IDS) pharmacy for each subject. For sites outside PENN, medication counts will be done by the site or site pharmacy.

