The usual protocol for opioid detoxification is tapering doses of methadone or buprenorphine, or suppressing autonomic over activity with an alpha 2 adrenergic agonist, such as clonidine or Lofexidine (LFX). The use of α agonists as adjuncts gained popularity when early studies found that withholding a single dose of clonidine prior to anesthesia caused a patient to experience an acute hypertensive crisis (Brodsky and Bravo, 1976) and it was theorized that α -2 agonists reduce withdrawal effects in the central and peripheral nervous systems. Centrally within the locus coeruleus, α agonists were able to produce sedation, analgesia and mild euphoric effects, and partially block the sweating, rhinorrhea and objective signs of withdrawal in chronic opioid users but did not have much effect on the achiness, insomnia, dysphoria and other subjective symptoms.

Opioid tapers with methadone or buprenorphine are better tolerated compared to treatment with alpha 2 adrenergic agonists, but patients interested in XR-NTX treatment need a 7-14-day opioid-free interval to avoid having naltrexone precipitate withdrawal, thus leaving time to relapse. Clonidine avoids this problem (Gold et al, 1980) but does not have FDA approval for this indication, does not decrease the dysphoria and other withdrawal-related subjective effects, and is unpopular with patients and physicians alike. Studies by Ling et al (2005) are an example. They show that only 61% of inpatients randomized to clonidine detoxification remained in treatment and had opioid negative urines at day 13, vs 77% in a buprenorphine detoxified group. Results were even worse in outpatient settings where only 5% of clonidine treated patients completed detoxification vs. 29% of those treated with buprenorphine only.

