7.1.5 Detoxification with Lofexidine. A third detoxification approach emerged with the approval of LFX, a selective alpha 2 adrenergic agonist. Unlike clonidine, it has reduced potency at the A subtype of the alpha 2 receptor and is associated with less bradycardia and hypotension (Yu et al, 2008; Gowing et al, 2016). Though its effects are similar to clonidine, its better safety profile is an advantage, especially in outpatient settings where hypotension can be a problem (Kahn et al, 1997; Lin et al, 1997; Carnwarth & Hardman, 1998). Like clonidine, it does not target the withdrawal- related subjective effects, thus potentiating a greater likelihood for dropout. An inpatient study randomized OUD inpatients to detoxification using lofexidine or diazepam. Twenty-seven percent (15/55) of the diazepam patients completed 10 days of treatment, vs 46.4% (26/56) of the lofexidine patients, thus more effective than diazepam although with much room for improvement (Guo et al, 2018). In a pivotal study leading to FDA approval, lofexidine showed a small reduction in subjective effects compared to placebo (a 2-point difference on the SOWS-Gossop scale) with significantly greater rates of detoxification completion (41% vs 28%; Fishman et al 2018). Again, showing the need for improvement, particularly for patients transitioning to antagonist therapy.

7.1.6 Detoxification with Pregabalin and Lofexidine. Here we propose to see if PGB can be safely combined with LFX to better reduce the subjective effects of opioid withdrawal and increase the proportion that transition to antagonist treatment. Such an approach could lower the detoxification hurdle for patients who are interested in antagonist treatment or in settings where agonist treatment is unavailable or difficult to access, and reduce overdose risk for those who make the transition. This study, will attempt to identify a PGB/LFX combination that reduces withdrawal- related subjective effects without generating more SAE's than LFX, as a precursor to a larger trial. The combination of PGB and LFX may result in increased drowsiness, lightheadedness and trouble concentrating.

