This study is a phase II, double-blind placebo-controlled, study to examine whether: 1) PGB can be combined with LFX and reduce opioid withdrawal-related subjective effects; and, 2) if safe and effective, can the combination increase the proportion of OUD subjects who transition to XR-NTX. To investigate these objectives, preliminary data on the safety and tolerability of PGB/LFX dose sequencing, and the reduction of opioid withdrawal-related subjective effects, will be obtained in the current trial. We will use a two-arm comparison; PGB/LFX versus LFX/PGB-PLA. If the current trial shows that a PGB/LFX combination is likely to be safe effective, and reduces opioid withdrawal related subjective effects, we will conduct a second trial in which we will test the PGB/LFX combination in a larger sample, under well- powered conditions, to evaluate the results of the current trial in relation to the efficacy of the combination to reduce opioid withdrawal-related subjective effects and possibly increase the proportion of patients who complete detoxification and transition to XR-NTX treatment. The first 2-year component will utilize three sites with inpatient units. Each site will recruit around 30 randomized subjects for a total sample size of 90 using DSM-5 criteria to establish

OUD with physiologic features diagnosis.

This trial has 4 distinct phases (see 4.0: Figure 1 schematic): 1) Screening (up to 30 days before inpatient admission and randomization). Patients who were never randomized and who come back after 30 days must be reevaluated and assigned a new screening number; 2) Inpatient Detox (1 – 7) days for medication induction and other assessments, 3) Inpatient administration of XR-NTX (Day 8); and, 4) Outpatient Follow-Up (Day 10 and Day 15). Dosing for lofexidine and pregabalin will begin at 12:00 on day 1 and be tapered starting at day five. This plan will permit dose adjustments for adverse effects, such as BP <90 mmHg systolic or <60 mmHg diastolic, a clinically significant drop in standing vs sitting blood pressure, bradycardia <50 bpm, or excessive sedation. Subjects that need a procedure repeated can continue inpatient treatment through day 9. The Study Schema is seen above in 4.0, Figure 1: Overview of Study Schematics Pregabalin (LYRICA®) plus Lofexidine (LUCEMYRATM)". Study assessments are seen in 5.0 Table 1.

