19.2 MEDICATION DISCONTINUATION CRITERIA

All randomized subjects are included in the intent-to-treat analysis. All subjects who prematurely discontinue treatment will be scheduled for a final evaluation and end-of trial visit (unless these two fall within 2 weeks of each other), and the follow up visit. Subjects are not dropped from all study activity unless they request to not be contacted or cannot be located for assessment.

Subjects will be informed at the consent session that medications may be held or discontinued due to intolerable side effects, hypotension or other problematic cardiovascular effects, or extreme lab values confirmed by a repeat test. (AST or ALT levels greater than 4 times upper limit of normal; elevated BUN, creatine kinase, or other evidence of renal damage). Subjects will also be informed at the consent session that he or she may be discontinued from study treatment due to: 1) Development or exacerbation of significant psychiatric or medical symptoms which necessitate admission to a medical unit or an intervention different from that provided by the protocol; 2) Clinical deterioration for any reason or a clinical status which necessitates inpatient admission; 3) Prolonged QTc after repeat ECG; 4) Blood pressure is less than 90 mm Hg (systolic) or less than 60 mm Hg (diastolic). For sitting to standing blood pressure (orthostatic change), if there is a change in systolic blood pressure of more than 20mm or diastolic blood pressure more than 10mm HG, the dosing nurse or physician may hold the lofexidine or pregabalin dose until the next dose and then recheck (can use manual blood pressure check if considered necessary). If at any point blood pressure is less than 90/60 the nurse or physician should also hold the lofexidine or pregabalin dose and consult a study physician. If for any dose, the blood pressure results remain below the previously stated minimum mmHg by the next scheduled dose, the next dose may be reduced or withheld. Dosing discontinuations can be discussed with the Lead PI and the medical monitor if it impacts subject continuation in the dosing part of the study. The reason the subjects misses their next dose of Study Medication or discontinues from Study Medication must be documented in the subject's casebook

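### The three tolerability outcomes in 13.5 are withdrawal symptoms, two of them items of the primary scale, and section 13 plans no comparison by arm of held or reduced doses, non-edema AE discontinuation, dizziness or SAEs

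*Combined protocol and SAP*

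**What the plan says.** Section 13.5 lists three tolerability outcomes:

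- Achiness: "Item 10 yields an ordinal measure of achiness".
- Anxiety: "Item 1 of the SOWS-Gossop yields an ordinal measure of anxiety".
- Insomnia: "The Insomnia Severity Index will be administered daily during detoxification, and yields a total score".

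Each is compared between arms by a mixed model. Section 13.3.1 makes the SOWS-Gossop total the primary efficacy outcome.

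On what the trial needs to learn, section 7.1.6 promises "preliminary data on the safety and tolerability of PGB/LFX dose sequencing" and seeks a combination that reduces subjective withdrawal "without generating more SAE's than LFX, as a precursor to a larger trial". The note in the Protocol Summary (3.0) says of the two drugs together that "it is likely that doses will need to be held or reduced due to side effects". Section 19.2 requires that the reason for a missed dose or for stopping study medication "must be documented in the subject's casebook".

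**The concern.** A tolerability outcome should get worse when patients cannot take the drug comfortably. These three get better when withdrawal is relieved, which is the effect pregabalin is added to produce. If pregabalin works, all three are expected to improve whether or not doses were often held for dizziness or low blood pressure. The report could then claim both efficacy and good tolerability from largely the same data. The trial is a precursor to a larger one, which section 7.1.6 makes conditional on the combination looking safe and effective. Readers of a tolerability result would take it as information on whether the regimen can be given as scheduled, and 13.5 does not measure that.

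**Working it through.** **What the three outcomes measure.** The plan gives no figure for tolerability, so this step is a comparison of sections.

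- Achiness and insomnia: section 7.1.2 says that alpha-2 agonists in chronic opioid users "did not have much effect on the achiness, insomnia, dysphoria and other subjective symptoms".
- Aches, anxiety and insomnia: the comfort-medication entry in 3.0 offers treatments for each of them as withdrawal symptoms that study medication has not suppressed.
- Overlap with the primary outcome: achiness and anxiety are 2 of the 10 SOWS items (section 10.11). Insomnia comes from a separate scale.

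**What section 13 compares by arm.**

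| Quantity | Planned comparison by arm |
|---|---|
| Sedation (POSS) | Yes, 13.4.2 |
| Creatine kinase, suicidality | Yes, 13.4.3 and 13.4.1 |
| Discontinuation for peripheral edema | Yes, 13.4.4 |
| Heart rate and blood pressure | Yes, 13.8, as maximum values, maximum change and time to maximum |
| Detoxification completion | Yes, 13.3.2, whatever the cause of failure |
| Doses held or reduced | None |
| Discontinuation for any other AE | None; 10.12 says such AEs will be considered, without a method |
| Dizziness or lightheadedness | None |
| SAEs | None |

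**How much the edema comparison can show.** Section 7.3.6 gives about 1% discontinuation for peripheral edema on pregabalin. If that rate applied here, 60 × 0.01 = 0.6 events would be expected in the pregabalin arm, and the chance of none would be 0.99^60 = 0.55.

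**What an added comparison could show, using dizziness.** Inputs: 60 versus 30 patients and two-sided alpha 0.05 (13.2); dizziness 29% at 600 mg/day and 5% on placebo (Table 4, diabetic neuropathy); dizziness at least 10% on lofexidine (7.4.3).

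At 29% versus 5%:

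- Expected patients: 60 × 0.29 = 17.4 and 30 × 0.05 = 1.5.
- SE = √(0.29 × 0.71/60 + 0.05 × 0.95/30) = 0.0708.
- 95% half-width = 1.96 × 0.0708 = 0.139, or about 14 points around a 24-point difference.

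Table 4 has no lofexidine background, whereas both arms here take lofexidine. Exact Fisher power by enumeration under several control rates:

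| Pregabalin arm | Control arm | Power |
|---|---|---|
| 29% | 5% | 0.81 |
| 34% | 10% | 0.71 |
| 29% | 10% | 0.52 |
| 39% | 15% | 0.63 |
| 29% | 15% | 0.27 |

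The 34% and 39% rows keep the 24-point excess. The 15% control rate is an assumption above the stated floor of 10%.

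**Discontinuation for any AE.** At the background rates of 14% and 7% (7.3.6), power is about 14% by the normal approximation and 9% by Fisher's test.

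**The case against.** The strongest reply is that harm is examined outside 13.5. The Protocol Summary names sedation as the most likely pregabalin effect, and hypotension and bradycardia as the most likely lofexidine effects. POSS and vital signs are both compared by arm. A patient who stops early and takes no day-7 dose falls in the lowest category of the ordinal outcome in 13.3.2. The DSMB sees unblinded adverse events (19.1) and reviews the protocol at the second medication-associated SAE (23.2).

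Much of this stands. A reader might infer that the plan cannot show harm at all, or that stopped medication is never compared. The documents support neither reading: the comparisons above exist, and 13.4.4 compares discontinuation for edema. A reader might also infer that 13.5 decides whether the larger trial goes ahead. No rule in the documents says so, and its outcomes are neither primary nor secondary.

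The reply leaves a gap, however. The summaries in 13.8 are maxima, which do not directly show low blood pressure or pulse. The completion outcome does not separate intolerance from other causes. DSMB review is oversight during the trial, not a reported comparison.

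It could also be said that aches, anxiety and poor sleep describe how tolerable detoxification is as a whole. That is a fair clinical use of the word, but section 7.1.6 promises tolerability of the dosing sequence, and these outcomes do not isolate it.

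**Conclusion.** The point holds in a confined form. Section 13.5 uses the wrong construct: its three outcomes are withdrawal symptoms on the protocol's own account, and two of them are already in the primary total. A withdrawal benefit would be reported a second time as tolerability. The expected holding and reducing of doses, discontinuation for AEs other than edema, dizziness, and the stated SAE aim have no planned comparison by arm. The primary test is unaffected, and so are the safety comparisons in 13.4 and 13.8.

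The size of any tolerability difference cannot be derived from the documents, which give no rate of held doses and no rates for the combination. A reader might take the 81% power for dizziness as what this trial could deliver. That figure rests on pregabalin versus placebo in another population without lofexidine, and it falls to 52% at 29% versus 10% and 27% at 29% versus 15%. The missing comparisons are therefore worth reporting as estimates, not as tests. The point should be corrected before analysis but does not threaten the trial.

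**What to change.** Relabel achiness, anxiety and insomnia as withdrawal-symptom (exploratory efficacy) outcomes, with their models unchanged. Define tolerability in 13.5 by arm as:

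1. the proportion with at least one dose held or reduced for an AE, separately for pregabalin/placebo and lofexidine;
2. the percentage of scheduled dose taken, for each drug;
3. the proportion stopping either drug for any AE;
4. the proportion with dizziness or lightheadedness;
5. the proportion with any SAE.

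Give risk differences with 95% confidence intervals, and a mean difference with its interval for item 2. State that these are descriptive and carry no significance claim.

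The data are already recorded: blister-pack adherence (Table 1 footnote), AE codes, seriousness and action taken on study drug (13.7), and reasons for missed or stopped doses (19.2). No new visits, patients or changes to dosing rules are needed. The cost is some SAP wording and a few more exploratory tables.

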
Outpatient screening is used to determine eligibility for the study. It will consist of the 30 days prior to inpatient admission for study detoxification and treatment. On day 1 of inpatient treatment subjects will be randomized to PGB/LFX or PGB-PLA/LFX for a 7-day detoxification. On day 8, if the patient completes **Duration of subject** detoxification, continues to be interested in XR-NTX treatment, provides a urine, participation and and passes a naloxone challenge, he/she will be offered one injection of XR-NTX before hospital discharge. This injection of XR-NTX is optional. If retests must be medication administration done, such as a repeat of the naloxone challenge, all subjects are eligible to remain inpatient until Day 9. All subjects, whether they receive XR-NTX or not. will be referred to continuing care and asked to return to the research outpatient clinic on days 10 and 15 for follow-up visits. Subjects who cannot find a provider may be offered an additional XR-NTX injection up to 5 weeks after the Day 8 injection. Reference therapy PGB-Placebo plus lofexidine The primary outcome is reduction in subjective withdrawal as measured twice/day using the Short Opiate Withdrawal Scale (SOWS- Gossop). SOWS scores range from zero to 30. Groups will be compared on 10 or more repeated SOWS responses during inpatient treatment using linear mixed-effects regression models. The SOWS total will be regressed on a three-level factor for site, and a two-level factor for pregabalin dose, with random intercept and correlated residuals and a random slope included if necessary for fit. Contrasts Statistical between the combined groups will be estimated from this model. Methodology The secondary outcome is an ordinal response indicating completion of detox and receipt of antagonist treatment, with levels (1) failure to complete detox, (2) completion of detox with failure to receive antagonist treatment, and (3) completion of detox and receipt of antagonist treatment.

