7.1.3 Detoxification with Buprenorphine. Combining low and decreasing doses of buprenorphine with low and increasing doses of oral naltrexone was also studied as a way to transition to naltrexone and the results were positive in an early study where 56% in the experimental group transitioned to XR-NTX vs 33% in the buprenorphine group (Sullivan et al, 2017). However, a larger trial of 378 patients randomized to one of three regimens: NTX + BUP; NTX + placebo BUP (PBO-B); placebo NTX (PBO-N) + PBO-B found no difference in transition to XR-NTX across groups (41-46%), although for those inducted onto XR-NTX, the management of opioid withdrawal symptoms prior to starting XR-NTX was achieved in a structured outpatient setting using a well-tolerated, fixed-dose ancillary medication regimen common to all three groups. (Bisaga et al, 2018).

7.1.4 Detoxification with Pregabalin. During the time that PGB was available without a prescription in Russia, clinicians observed that opioid addicted patients were using it to suppress withdrawal when their heroin supply ran out. These observations led to a study in which 34 heroin-addicted patients were randomized to detoxification protocols using PGB alone, or clonidine alone (Krupitsky et al, 2017). While groups did not differ on baseline clinical or demographic features, 15 of the 19 PGB subjects completed treatment (79%) compared to 7 of 15 (47%) in the clonidine group (p = 0.05, Fisher exact test), and a Kaplan-Meier Survival Analysis confirmed better retention in the PGB group (p = .001). There was no significant group difference in reduced severity of withdrawal, however the pregabalin group reported less opioid craving (p= .05), less anxiety (p=0.05), less depression (p=0.05), and higher assessments of general health (p < 0.05). Ketorolac was available as needed for pain, and the average dose of symptom-triggered ketorolac in the clonidine group was almost twice that of the PGB group (60.5 \pm 8.2mg vs. 36 \pm 7.8mg, (p< 0.05). In addition, the PGB group reported less fatigue compared to the clonidine group (16% vs. 47%, p < 0.05) and there was no significant difference in AR's between groups. These findings were consistent with studies using rodent models that demonstrated PGB attenuates opioid withdrawal (Vashchinkina et al 2017).

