13.3 STATISTICAL METHODS

13.3.1 Primary Outcome - Reduction in SOWS-Gossop criterion. The primary outcome will be reduction in subjective withdrawal as measured by the SOWS - Gossop (scores range from zero to 30). The groups will be compared on the 14 repeated SOWS-Gossop responses obtained during the seven-day detoxification period, using linear mixed-effects regression models; the SOWS-Gossop total will be regressed on a three-level factor for site, and a two-level factor for medication group, with time and group by time effects. The covariance structure will include a random intercept and correlated residuals, with a random slope included if necessary for fit. Contrasts between the PGB group and the PGB-PLA group will be estimated from the model. Exploratory analyses of heterogeneity of dose effects across sites will be performed including a site by dose interaction term in the main model.

These models will provide valid estimates and tests if any missing data is statistically ignorable (Laird, 1998). Dropout may be associated with reports of subjective withdrawal, and will be ignorable if available subjective scores prior to dropout are predictive of dropout. To assess possible effects of non-ignorability on inference, we will perform sensitivity analyses using pattern- mixture models and selection models. For pattern mixture models, subjects are grouped on the basis of their pattern of missing data. Usually, rarely occurring patterns are grouped, so as to keep the number of pattern-groups at a manageable level. This grouping defines a nominal variable, which is then used as a predictor in the analyses, although a covariate representing missingness on a continuous scale can also be used. The regression coefficients associated with this variable, and its interactions with the other predictors, quantify how response-predictor relationships differ across the different patterns of missingness. Overall predictor effects may be found by averaging over the patterns (Little, 1993). For longitudinal data, subjects are usually stratified according to the visit after which they dropped out. Hedeker and Gibbons (1997), and Hedeker and Rose (2000), apply these methods to mixed effects models in longitudinal data. Selection models (Little, 1995; Kenward, 1998; Verbeke and Molenberghs, 2000) take a different approach, by explicitly modeling the probability of drop out, and incorporating the predicted probabilities

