13.4 SAFETY OUTCOMES

- 13.4.1 Suicidality. We will compare the groups on presence of active suicidal ideation on the basis of the C-SSRS, which will be administered daily. We define Active Suicidal Ideation to be an endorsement of either Question 4 (active ideation without plan) or 5 (active ideation with plan). If there is sufficient variability in these repeated binary outcomes, we will compare the groups using a mixed effects logistic regression model, similar to the linear mixed effects models described above for the primary outcome; if variability is too low, we will use a (non-mixed-effects) logistic regression model to compare the groups on proportion of participants reporting active ideation at any time in the period
- **13.4.2 Sedation.** The POSS will be administered four times a day on dose days, yielding a set of repeated measures on the POSS score for each participant. We will compare the groups on this score, using linear mixed effects models similar to those described above for the primary outcome.
- **13.4.3** Elevated Creatine Kinase. On day 8 of detoxification, participants will be classified as having elevated creatine kinase if their level is more than three times their screening level. We will compare groups on this response using a logistic regression model with site and group as explanatory variables.
- **13.4.4_Edema**. We will compare groups on the proportion of participants whose study medications were discontinued due to peripheral edema, using a logistic regression model with site and group as the explanatory variables.

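### The achiness and anxiety models (13.5.1, 13.5.2) name site and group but not time; fitted that way, the group odds ratio can lean toward the arm that keeps patients longer

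*Combined protocol and SAP*

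**What the plan says.** Section 13.5.1 compares the arms on SOWS-Gossop item 10 (achiness) using "mixed effects ordinal logistic regression models, with site and group as the main explanatory variables". Section 13.5.2 treats item 1 (anxiety) by reference: "we will compare the groups using mixed effects logistic regression models as for the Achiness item above". No fuller statement of either model appears elsewhere.

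The other repeated measures are handled differently. Section 13.3.1 gives the primary model "a two-level factor for medication group, with time and group by time effects", applied to the "14 repeated SOWS-Gossop responses obtained during the seven-day detoxification period". Sedation (13.4.2) uses "linear mixed effects models similar to those described above for the primary outcome" and insomnia (13.5.3) uses "linear mixed effects models similar to those described for the primary outcome". The repeated-measures form of the suicidality analysis (13.4.1) also points back to the primary model. Achiness and anxiety are the only repeated outcomes in 13.3 to 13.5 whose regression predictors are listed on their own, without time.

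**The concern.** Both items are rated up to 14 times during a week in which withdrawal is expected to ease; section 13.2 powers the trial on how fast the SOWS falls. A patient who leaves on Day 3 contributes only early, worse ratings. A patient who stays contributes the later, milder ones as well. With no time term, the model has only the group coefficient and the random intercept to explain the fall. If one arm stays longer, some of the ordinary resolution of withdrawal is credited to treatment.

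Unequal retention is not remote here, because better completion on pregabalin is a secondary objective (8.2). Section 7.1.4 also cites a trial in which "15 of the 19 PGB subjects completed treatment (79%) compared to 7 of 15 (47%) in the clonidine group". At stake is the reading of two named tolerability outcomes.

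**Working it through.** **Inputs from the protocol.** 60 versus 30 patients, two-sided 5%, 40% overall dropout not split by arm, within-patient correlation 0.5 (13.2). 14 readings (13.3.1). A 10-item scale (10.11) with a 0-30 total implies 30/10 = 3 as the item maximum, so four levels. Illustrative completion is 15/19 = 79% and 7/15 = 47% (7.1.4).

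**Assumptions not in the protocol.** Random-intercept SD of 1.5 logits, the thresholds, the daily fall on the logit scale, and completion by arm.

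**1. The plan's own figure.** No figure is given for the item models. The nearest is 80% power at d = 0.44 for the primary group-by-linear-time effect. Generalised least squares with 14 occasions, compound symmetry 0.5 and retention falling linearly to 60% gives a detectable d of 0.450.
- Standard error = 0.450/(1.960 + 0.842) = 0.1606.
- Power at 0.44 = Φ(0.44/0.1606 − 1.960) = Φ(0.78) = 78.2%.

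Other dropout codings give 77.0% to 78.9%. The figure is essentially reproduced for a model that contains time.

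**2. Rough size of the shift.** Number the days 0 to 6 and let a constant fraction r remain each day, so r = 0.79^(1/6) = 0.961 and 0.47^(1/6) = 0.882.
- Weighting every reading equally, the mean day is Σk·r^k / Σr^k = 17.74/6.24 = 2.84 versus 12.40/4.95 = 2.50. The gap is 0.34 day.
- Weighting every patient equally, the mean day is ½Σr^k for k = 1 to 6 = 2.62 versus 1.98. The gap is 0.64 day.
- At 0.5 logit per day the shift is 0.34 × 0.5 = 0.17 to 0.64 × 0.5 = 0.32 logits. As odds ratios, exp(−0.17) = 0.84 and exp(−0.32) = 0.72.

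A random-intercept model weights patients somewhere between these two schemes.

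**3. Simulation with no true group effect.** Random-intercept cumulative logit, 300 trials per scenario, Monte Carlo error 0.02 to 0.03 on the log scale. Odds ratios below 1 favour pregabalin.

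| Completion, PGB/placebo | Course of item | OR, no time | OR, with day |
|---|---|---|---|
| 79/47 | falls 0.5 per day | 0.80 | 1.03 |
| 79/47 | falls 0.25 per day | 0.89 | 1.01 |
| 79/47 | Day 3 peak, then falls | 0.83 | 0.98 |
| 79/47 | flat | 1.03 | 1.04 |
| 70/40 | falls 0.5 per day | 0.78 | 0.99 |
| 65/50 | falls 0.5 per day | 0.90 | 1.00 |
| 60/60 | falls 0.5 per day | 1.04 | 1.04 |
| 70/40, severe leave first | falls 0.5 per day | 0.86 | 1.10 |
| 70/40, severe leave first | falls 0.25 per day | 0.96 | 1.10 |
| 70/40, severe leave first | falls 0.1 per day | 0.96 | 1.03 |

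The flat and 60/60 rows should give 1 and give 1.03 to 1.04, so differences of that size mean nothing. Two separately coded simulations of the 79/47 case gave mean log odds ratios of −0.20 (OR 0.82; total fall 3 logits over the week) and −0.18 (OR 0.84; 0.5 per day). A smaller run of 200 trials gave 0.77.

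**4. False positives at nominal 5%, 79/47.** The tabulated simulation did not hold its level even where no bias exists, so its rejection rates are not used. The two others held it:
- 220 trials: about 9% without time and about 4% with it; equal completion about 4%.
- 250 trials: 27/250 = 10.8% without time (26 of the 27 favouring pregabalin) and 5.2% with it; equal completion 4.8%.

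Monte Carlo error is about 2 points.

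**5. Against sampling error.** The empirical SD of the log odds ratio at 79/47 with a fall of 0.5 per day is 0.36, so the bias is 0.222/0.36 = 0.6 of a standard error.

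**The case against.** **Silence is not exclusion.** A reader might infer that the plan rules time out. It does not. Section 13.5.1 calls site and group the *main* explanatory variables, whereas the creatine kinase, edema and ordinal secondary models list theirs without that word. The Protocol Summary describes the primary model through "a two-level factor for pregabalin dose, with random intercept and correlated residuals" and also leaves time out, although 13.3.1 shows that the model has it. The omission may be shorthand. What stands is that 13.5 is the only specification of these models, and an analyst following it literally would fit no time term.

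**The cited pregabalin trial is not a null precedent.** A reader might infer that it showed better retention with no symptom benefit, so that any benefit seen here would be false. It found no significant difference in withdrawal severity, but section 7.1.4 also reports less anxiety on pregabalin (p=0.05) and almost twice the ketorolac use on clonidine. It had 34 patients and tested pregabalin alone against clonidine alone, not as an add-on to lofexidine. It serves only as an example of unequal retention.

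**A false benefit is not the expected result.** In the main scenario about 9 in 10 null trials would still be non-significant. Larger figures come from pairing 41% completion on lofexidine (7.1.5) with 79% on pregabalin, but those arms belong to different studies, so they are not relied on here.

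**Dropout may depend on symptoms**, as 13.3.1 accepts. The bias without time is then smaller, and a time term does not give an exact answer either (up to 1.10 in the table; at a fall of 0.25 per day that is further from 1 than 0.96). Time removes the part due to unequal length of observation, not the part due to severity-driven dropout. The sensitivity analyses for the latter are described only for the primary outcome.

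**Conclusion.** The point holds in conditional form. As written, 13.5.1 and 13.5.2 do not state a time term that every comparable repeated-measures model in the plan has directly or by reference. If none is fitted, the group odds ratio can be biased toward the better-retained arm. At 79% versus 47% completion, a fall of about 0.5 logit per day and dropout unrelated to the item, the odds ratio is about 0.80 to 0.84 when the truth is 1, with about 9 to 11% false positives.

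Those figures rest on the assumed fall, the intercept SD and the borrowed retention rates. There is no bias with equal retention or a flat course, and less with a slow fall or with severe patients leaving first.

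A reader might infer that the main efficacy result is at risk. It is not: the primary model contains time, and the ordinal secondary outcome is measured once per patient. Only two single-item tolerability outcomes are affected, and 13.2 attaches no power claim to them. Severity is minor, but the plan should settle the matter before unblinding because doing so costs nothing.

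**What to change.** In 13.5.1, state the fixed effects as in 13.3.1 (site, group, time and group by time), and let 13.5.2 inherit them. With an interaction in the model, the group coefficient alone is the difference at whatever time is coded zero. So name the reported quantity: the pregabalin versus placebo contrast averaged over fixed Days 1-7. Coding day as a factor is optional; a linear term would match 13.2.

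Extending the missing-data sensitivity analyses of 13.3.1 to these two items would help with severity-driven dropout, but is a separate and optional step.

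The cost is one line of text. No new data, visits or patients are needed, and nothing changes if time was always intended.
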